## iib. Innovation

This proposal for additional funding represents innovative work on three levels:

### iib-1) One-stage ADM assisted implant reconstruction

Although multiple recent case series have demonstrated the feasibility of using AlloDerm in immediate one-staged prosthetic breast reconstruction, this technique is still relatively novel and early in its practice. In addition, several authors have observed improved aesthetic outcomes with the use of ADM in implant-based breast reconstruction. Spear et al found that greater expansion in the lower breast pole can be achieved with the use of AlloDerm. He hypothesized that greater expansion in the lower pole allowed for the creation of a breast with greater ptosis and more natural breast contour. Breuing et al observed that the AlloDerm sling created a sturdy, elastic sling that was strong enough to support the weight of the permanent implant preventing undue traction on the inferior mastectomy flap and at the same time reduced excessive upper-pole fullness. In addition, Salzberg observed in his large series of 76 immediate ADM-assisted breast reconstructions that visible implant rippling was prevented with the interposition of AlloDerm even in patients with thin mastectomy skin flaps.

### iib- 2) Breast Q©

Traditional assessments of outcome in breast reconstruction have included an evaluation of complication rates and aesthetic results from a surgeon's perspective. Despite the recent emphasis on the importance of patient-reported outcome measurements, few instruments exist that are designed to accurately measure breast surgery outcomes from a patient's perspective. The recent development of the Breast Q©, a prospectively designed and validated patient reported outcome questionnaire for breast reconstruction has provided us with reliable information about the success of surgery from the patient's perspective. Using the Breast Q© as the primary outcome measure, this study aims to compare patient satisfaction between women receiving one-stage immediate breast reconstruction facilitated by ADM and those receiving the conventional two-stage TE/implant reconstruction without ADM. To date, there has been no prospective randomized trial comparing the efficacy, safety, aesthetic outcome, cost effectiveness, and most importantly patient-reported satisfaction between the ADM assisted one-stage reconstruction with the conventional two-stage reconstruction.

### iib-3) Cost effectiveness analysis

Despite the importance of cost effectiveness analysis (CEA) in evaluating health outcomes and resource costs in surgical interventions, there is a paucity of this research in the area of post-mastectomy reconstruction. Paramount in the CEA, is not only considerations of direct and indirect cost of intervention, but also patient perception of their health outcome (utility) and complications or morbidity as a consequence of the intervention. This sister analysis can be easily added to our current ongoing RCT, since we are already prospectively collecting information on both short- and long-term complications, patient satisfaction and QOL as part of the study protocol. In addition, we will add the EQ-5D QOL instrument that addresses 5 dimensions to evaluate the health status as reported by patients at the same time-points as the Breast Q©. Cost effectiveness analysis will be performed on **person-level cost** (direct and indirect) and **effect** data (Breast Q© global score and utility value on EQ-5D) using **net benefit regression**, a novel technique developed by our collaborator.([name]) The cost data will come from hospital cost accounting systems and patient

reports. Accurate case costing information is collected by the Accounting Department of the hospitals with each patient visit to the ambulatory clinic, emergency department, operating room, or in-patient ward. The primary patient outcome measure will be the global Breast Q© score and the secondary outcome measure will be quality adjusted life years (QALY) as measured by the EQ-5D. The versatility of the net benefit regressions is that it can be modeled for a variety of monetary values with the probability of cost-effectiveness plotted against values for money on a cost-effectiveness acceptability curve. By eliminating the process of tissue expansion and a second operative procedure, we hypothesize that both the cost and utility as valued by patients will be superior in the 1-stage ADM method compared to the 2-stage TE/I method.

### iic. Approach

#### iib-1. Study Design

This **multi-center randomized controlled trial** will evaluate the impact of implantable human cadaveric acellular dermal matrix in the setting of immediate one-stage implant breast reconstruction. Three separate sites will participate in the trial (University Health Network, Women's College Hospital, and Vancouver General Hospital). Institutional Research Ethic Board approval has been obtained for all three sites.(APPENDIX 2) After obtaining informed consent and confirming eligibility both pre- and intra-operatively, patients will be registered in the study. Patients will be enrolled until there are 72 evaluable patients enrolled in each study arm. Stratification will be performed based on the laterality of the reconstruction (unilateral vs. bilateral reconstruction) at each of the three study sites. Patients who are deemed eligible pre-operatively by the investigating surgeon for the study will be **randomized** to undergo either **one-stage permanent prosthetic placement** with the use of implantable **acellular dermal matrix** or the conventional **two-stage TE/implant procedure** without the tissue substitute.

#### Study Schema:

Baseline Measure	Skin-sparing or Nipple-sparing mastectomy	Outcome Measure
Stratify by:		
1. Site	Acellular dermal matrix assisted one-stage implant reconstruction	1. Breast Q ©
UHN WCH VGH		2. EQ-5D
2. Laterality		3. Complications
Unilateral Bilateral		4. Aesthetics
	Two-stage tissue expander/implant reconstruction	5. Cost-effectiveness

The **primary outcome** evaluated will be **patient-reported satisfaction and quality of life** associated with the use of ADM in one-stage immediate prosthetic breast reconstruction following skin-sparing or nipple-sparing mastectomy. Patient-reported satisfaction and quality of life will be measured using the Breast Q© questionnaire. These questionnaires will be administered to patients prior to mastectomy, at two weeks following the mastectomy and immediate reconstruction, 6 months and one year (+/- 1 month) following completion of reconstruction. It is hypothesized that ADM assisted one-stage prosthetic breast reconstruction will be associated with improvement in patient-reported satisfaction and quality of life compared to the conventional two-stage TE/implant reconstruction.

The **secondary outcomes** will include **short and long-term complication rates**, overall **aesthetic outcome** including capsular contracture formation at six month and one-year following completion of the reconstruction, and a **cost effectiveness analysis (CEA)**. For the cost-effectiveness analysis, person-level cost and effect data will be collected throughout the study. The cost data will come from hospital cost accounting systems and patient reports. The patient outcome data will be collected at months 6 and 12 months post-mastectomy by the Breast Q© and EQ-5D. The primary measure of effectiveness will be the global Breast Q© score and the secondary measure will be quality adjusted life years (QALY) as measured by the EQ-5D. It is hypothesized that the short- and long-term complication rates will be comparable between the two study arms, while the overall aesthetic outcome will be superior with less severe capsular contracture in the ADM assisted one-stage than the two-stage TE/implant reconstruction. Lastly, we hypothesize ADM assisted one-stage implant reconstruction will be the more cost effectiveness method of implant reconstruction following mastectomy than the standard two-stage TE/I method.

Timing of Questionnaires

Questionnaire	Baseline	Mastectomy &	2 weeks postop	6 months postop	12 months postop
Breast Q©	XX	Immediate	XX	XX	XX
EQ-5D	XX	Breast Reconstruction		XX	XX

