1. To compare patient satisfaction and QOL between one-stage ADM and two-stage TE/I reconstruction without ADM following mastectomy. Patient satisfaction will be evaluated using the Breast Q© at two-weeks, as well as six months and one year following completion of reconstruction.

**Hypothesis:** Patient satisfaction and QOL will be higher in the ADM assisted one-stage implant reconstruction group compared to the two-stage TE/I group at all three time-points.

The **secondary objectives** of this study are:

1. To compare the short- and long-term complication rates between the two techniques.

**Hypothesis:** The use of ADM in one-stage prosthetic breast reconstruction is not associated with increased short- and long-term postoperative complications compared with the traditional two staged TE/I procedure.

2. To examine the overall aesthetic outcome achieved using the ADM facilitated one-staged breast reconstruction at six months and one year following completion of the reconstruction.

**Hypothesis:** The overall aesthetic outcome achieved using the ADM facilitated one-stage breast reconstruction is superior to that following the two-stage breast reconstruction.

3. To perform a cost-effectiveness analysis (CEA) of the two reconstruction methods using the net benefit regression model on person-level cost and effect data collected during the study.

**Hypothesis:** Both the direct and indirect cost will be reduced and patient-reported utility will be greater for the one-stage ADM method compared to the TE/I method.

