## **iib-8. Outcomes and their measurements**

### **Primary Outcome: *Patient-Reported Satisfaction and Quality of Life***

Patient satisfaction and quality of life will be measured using the Breast Q $\circ$  as a self-administered questionnaire. The Breast Q $\circ$  has 2 subscales that examine the two different domains: satisfaction and psychosocial function. The scores generated for each subscale will be transformed on a scale from 0-100, lowest to highest summary scores respectively. Scale validity and reliability are supported by the high Cronbach's alpha coefficient (>0.80) and intra-class correlation coefficients (>0.70). The scores generated for each subscale will be transformed on a scale from 0-100, lowest to highest summary scores respectively. Participants will be asked to complete the pre-operative module of the Breast Q $\circ$  questionnaire at 2 weeks prior to the mastectomy.(APPENDIX 4) Post-operatively, they will be requested to complete the post-operative module of the Breast Q $\circ$  at 2 weeks following immediate reconstruction, as well as 6 months and 1 year following the completion of the reconstruction. (APPENDIX 5) The questionnaires will be self-administered and mailed to the participants with return envelopes and prepaid postage. To compensate our study patients for their participation, a monetary reimbursement (\$10) will be available upon completion. The Dillman method will be used to encourage patient response.

The **secondary outcomes** will include a comparison of:

1. **short and long-term complication rates**: Short-term complications are intra- and post-operative complications occurring within two months of surgery and long-term complications occur later than two-months. They will be documented and collected prospectively.

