2. **long-term aesthetic result**: Evaluation of the overall aesthetic result and capsular contracture grade will be performed at six months and one year following the completion of reconstruction. A routine physical examination will be performed by the attending surgeon and photographic documentation (5 standardized photographs) of the reconstruction will be obtained at the six month and one-year follow-up visit. A panel of three independent, blinded observers will subsequently evaluate the overall aesthetic result using the three-point, five item, Breast Aesthetic Score described by Lowery with the use of photographic documentation. Capsular contracture will be graded by the examining physician and will be graded using the Modified Baker Scale for Reconstructed Breasts, which is widely accepted to be the gold-standard measure of capsular contracture grade.
3. **cost-effectiveness**: Costs and effects will be simultaneously analyzed by collecting person-level cost and effect data. The cost data will come from hospital cost accounting systems and patient reports. The patient outcome data will be collected at months 6 and 12 months post-mastectomy by Breast Q $\circ$

and EQ-5D. The frequently used generic HRQoL instrument EQ-5D will be piggy-backed to the Breast QoL at the 2 post-mastectomy time-points to generate a utility value for current health. The primary measure of effectiveness will be the Breast Q score and the secondary measure will be quality adjusted life years (QALY) as measured by the EQ-5D (APPENDIX 6)

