### **9c. Measurement of the Primary Objective:**

#### ***i) Primary Analysis***

Each of the two domain-specific summary scores on function and satisfaction will be transformed on a scale from 0 to 100 using RUMM software. Mean scores and standard deviation for each surgery group will be calculated and compared. To address our primary aim of comparing patient satisfaction and quality of life between **Group 1** (one-stage with ADM) and **Group 2** (two-stage group without ADM) before and at the three post mastectomy follow up reference time points, we will use the **repeated measure analysis** to examine the time effect and time-group interaction. In all analyses, statistical significance will be designated at  $p <= 0.05$  level.

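### Six- and 12-month outcomes are timed both from completion of reconstruction and from mastectomy, which are different dates in the two-stage arm, and costs and long-term complications have no per-patient end

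*Combined protocol and SAP*

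**What the plan says.** - **Breast Q, collection.** The primary objective (section i) places the later forms "as well as six months and one year following completion of reconstruction". The Study Schema text gives "at two weeks following the mastectomy and immediate reconstruction, 6 months and one year (+/- 1 month) following completion of reconstruction", and section iib-8 gives "at 2 weeks following immediate reconstruction, as well as 6 months and 1 year following the completion of the reconstruction".
- **Breast Q, analysis and economics.** Section 9c i compares the arms "before and at the three post mastectomy follow up reference time points". For Breast Q and EQ-5D together, the cost-effectiveness part of the Study Schema text says: "The patient outcome data will be collected at months 6 and 12 months post-mastectomy". Section iib-8, item 3, repeats this.
- **EQ-5D.** The only origin stated outright is mastectomy (Study Schema text; iib-8, item 3). Section iib-3) Cost effectiveness analysis, under Innovation, has health status "as reported by patients at the same time-points as the Breast Q", which ties EQ-5D indirectly to the completion clock.
- **Questionnaire table.** The last column reads "12 months postop". It names no operation, but the follow-up columns come after one for mastectomy with immediate reconstruction.
- **Aesthetics.** Under section iib-8, item 2, the evaluation "will be performed at six months and one year following the completion of reconstruction". Section 9c ii analyses the Breast Aesthetic Score at 6 and 12 months after mastectomy.
- **End of observation.** Section 9c iii counts the costs that build up in the study period. Section iib-8, item 1, treats any complication after two months as long-term. Neither gives an end date per patient, and item 1 does not say which operation starts the clock in an arm that has two.

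**The concern.** The two origins are not interchangeable between arms. Group A receives the permanent implant at the first operation. Section iib-6 gives every Group B patient a later exchange operation. The choice of clock therefore moves the two-stage visits and, absent later surgery, leaves the one-stage visits where they are.

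Three things depend on it:

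- The repeated-measures analysis examines time and the time-by-group interaction, but time has no single meaning. On the mastectomy clock a two-stage patient may answer the 6-month form before or after exchange. On the completion clock she always answers it six months after.
- In section 9c iii net benefit is effect times its money value, minus cost. The length of the cost window therefore enters the result directly.
- Long-term complication rates are compared by chi-square or binomial test, and neither allows for unequal follow-up.

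**Working it through.** The documents state no figure for the gap between the origins, so there is none to reproduce. The sample size does reproduce and does not depend on this point: 2 x (1.960 + 1.036)^2 x 20^2 / 10^2 = 71.8, so 72 per arm at 85% power and two-sided alpha 0.05.

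**Inputs**
- First inflation at week 2, then biweekly; exchange about 3-6 months after inflation ends, or 4-6 weeks after chemotherapy (section iib-6).
- Number of sessions: assumed to be 5. The preliminary cost data in iia-3 report on average 5 more clinic visits in the two-stage arm, from a 10-patient review.
- Biweekly is read both ways, as every two weeks and as twice a week.
- Completion is taken as permanent implant placement (assumption).
- Visit window: +/- 1 month (Study Schema text).
- 1 week = 7/30.4375 = 0.230 month.

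**Formula (no-chemotherapy route).** Mastectomy to exchange = [2 weeks + interval x (sessions - 1)] + 3 to 6 months.

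- One session: 2 x 0.230 = 0.46; 0.46 + 3 = 3.46 months at the short end.
- Five sessions, every two weeks: 2 + 2 x 4 = week 10 = 2.30 months; exchange at 5.30-8.30 months.
- Five sessions, twice a week: 2 + 0.5 x 4 = week 4 = 0.92 months; exchange at 3.92-6.92 months.

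**Two-stage visits in months after mastectomy, five sessions**

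| Quantity | Every two weeks | Twice a week |
|---|---|---|
| Exchange | 5.30-8.30 | 3.92-6.92 |
| 6 months after completion | 11.30-14.30 | 9.92-12.92 |
| 12 months after completion | 17.30-20.30 | 15.92-18.92 |
| Last visit / 12 months | 1.44-1.69 | 1.33-1.58 |
| 12 months minus exchange | 3.70-6.70 | 5.08-8.08 |

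In the one-stage arm the offset is 0 absent later surgery, so its last visit is at 12 months on either clock. A 6-month post-mastectomy visit in the two-stage arm falls between 6 - 3.92 = 2.08 months after exchange and 8.30 - 6 = 2.30 months before it.

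**Chemotherapy route.** 4-6 weeks is 0.92-1.38 months, to be added to a chemotherapy start and duration that the documents do not give. It cannot be computed.

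**Direction.** The primary effect in the cost-effectiveness analysis is the Breast Q score, a level that does not accumulate with time. Extra two-stage months add cost with no added effect, and they add opportunity for complications. QALYs do accumulate, so the secondary analysis has a partial offset.

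**The case against.** The strongest reply is that there is only one schedule, loosely labelled. Section iib-8 attaches the EQ-5D to the Breast Q mailing, the Innovation section gives both the same time-points, and the table has a single set of columns. This largely stands as an account of intent. A reader might infer that the cost-effectiveness sentences set up a second, separate round of questionnaires; the documents do not establish that. But a single schedule still needs one origin, and the text gives two. The link in the Innovation section is itself loose, because the table has no EQ-5D at two weeks.

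A reader might also infer that the completion clock is the true one and that the post-mastectomy wording is a slip. The table points the other way, since its follow-up columns come after the mastectomy column. The choice is the sponsor's.

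It is fair to object that the gap rests on an assumed session count, on an undefined term and on intervals given as approximate. The session count matters little to the conclusion: even one session puts the gap at about 3.5 months on the no-chemotherapy route.

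Finally, a reader might infer that forms have already been lost for the 24 two-stage patients randomized when the preliminary data were written (16 + 8). The documents do not show this. Randomization is preoperative, and nothing records which forms had fallen due.

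**Conclusion.** The timing rules cannot all be followed as written. Breast Q and the aesthetic score each carry two origins, EQ-5D carries a second one indirectly, and completion is undefined. If completion means permanent implant placement, the origins agree in the one-stage arm absent later surgery. On the no-chemotherapy route of the two-stage arm they differ by about 3.5 months with one session and, assuming five, by 5.3-8.3 or 3.9-6.9 months depending on the meaning of biweekly. A +/- 1 month window cannot absorb that.

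The follow-up imbalance is conditional. Only if costs and long-term complications run to the last post-completion visit are two-stage patients observed about 1.3-1.7 times as long.

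A reader might infer that the direction of bias is then unknown because benefits accrue as well as costs. That holds only in part, for the secondary QALY analysis. In the primary cost-effectiveness analysis, and in the comparison of long-term complications, the imbalance favours the one-stage arm. For the Breast Q comparison itself the documents give no basis for a direction.

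**What to change.** 1. Define completion of reconstruction and state one time origin for each outcome. Make these places agree: the objectives in section i, the Innovation section on cost effectiveness, the Study Schema text, the questionnaire table, iib-8, and 9c i and ii. Which origin to keep is the sponsor's decision.
2. Count costs, QALYs and long-term complications over the same fixed period from mastectomy in both arms, and write that period into 9c iii and iib-8. Twelve months would match the cost-effectiveness text already there. Say which operation starts the two-month complication window. Results to the last visit can be supportive.
3. If questionnaires stay on the completion clock, state how the cost-effectiveness analysis obtains its effect values inside the fixed window. Under the five-session assumption, two-stage forms would fall at 9.9-14.3 and 15.9-20.3 months after mastectomy, so at most one lies within 12 months.

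The cost is mainly wording. Hospital costs are recorded visit by visit and can be cut at a fixed date. The price in information is that a 12-month window leaves only about 4-8 months after exchange under the five-session assumption, and some exchanges after chemotherapy may fall outside it. The report should say how many do.

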### iib-2. Patient Recruitment

Suitable participants will be identified by two Research Assistants (Toronto and Vancouver site) from the breast reconstruction clinics at the three study sites. All eligible participants will be accrued at the surgical centers to reach a target enrollment of 72 per arm. (Sample Size) Since our trial opened recruitment at the two study sites in Toronto in September 2009, a total of 67 women have been enrolled into the RCT. With the third site, Vancouver General Hospital joining the trial in January 2011, we anticipate that it would take until August 2011 to complete patient accrual.

### iib-3. Eligibility

Eligibility will first be determined at the time of the pre-operative consult according to the inclusion/exclusion criteria outlined below:

